# 2.3 Benefit/Risk Assessment

It cannot be guaranteed that participants in clinical studies will directly benefit from treatment during participation, as clinical studies are designed to provide information about the safety and effectiveness of an investigational medicine.

POS has been shown to be of benefit in the treatment of IA and other IFIs in controlled as well as uncontrolled studies and in salvage therapy studies using the IV, tablet, and oral suspension formulation in adults, and the IV and PFS formulation in pediatric participants [Walsh, T. J., et al 2007] [Lehrnbecher, T., et al 2010] [Maertens, J. A., et al 2021] [Groll, A. H., et al 2020]. In addition, literature reports of POS IV and tablet have indicated the benefit of the POS when used to treat mold infections, including IA, in high-risk patients [Conant, M. M., et al 2015] [Jeong, W., et al 2016]. The most common toxicities that have been reported with POS include gastrointestinal events (diarrhea, nausea, and vomiting), fever, headache, and cough. The following risks have been identified in patients treated with POS per product labeling: hypersensitivity, hepatic toxicity, QTc prolongation, and drug interactions. Refer to current POS (NOXAFILTM) product labeling for additional information. The safety and efficacy of POS in children <2 years of age has not been established. Current product labeling indicates approval in children 2 years of age and older and adults.

Additional details regarding specific benefits and risks for participants participating in this clinical trial may be found in the accompanying IB and informed consent documents.

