#### **Diagnostic Assessments**

- 11. Has QTc prolongation (based on either Fridericia or Bazett's correction) at screening >500 msec.
- 12. Has significant liver dysfunction (defined as total bilirubin  $>1.5 \times$  ULN AND AST or ALT  $>3 \times$  ULN with normal alkaline phosphatase) at screening.

13. Has calculated creatinine clearance <20 mL/min/1.73 m^2 (modified Schwartz formula) at screening. Creatinine clearance will be calculated using the following equation:

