# 7 DISCONTINUATION OF STUDY INTERVENTION AND PARTICIPANT WITHDRAWAL

### 7.1 Discontinuation of Study Intervention

Discontinuation of study intervention does not represent withdrawal from the study.

As certain data on clinical events beyond study intervention discontinuation may be important to the study, they must be collected through the participant's last scheduled followup, even if the participant has discontinued study intervention. Therefore, all participants who discontinue study intervention before completion of the protocol-specified treatment period will still continue to participate in the study as specified in Section 1.3 and Section 8.9.2.3.

Participants may discontinue study intervention at any time for any reason or be discontinued from the study intervention at the discretion of the investigator should any untoward effect occur. In addition, a participant may be discontinued from study intervention by the investigator or the Sponsor if study intervention is inappropriate, the study plan is violated, or for administrative and/or other safety reasons. Specific details regarding procedures to be performed at study intervention discontinuation are provided in Section 8.1.9 and Section 8.9.2.3.

A participant must be discontinued from study intervention but continue to be monitored in the study for any of the following reasons:

- The participant or participant's legally acceptable representative requests to discontinue study intervention.
- The participant has a medical condition or personal circumstance, which, in the opinion of the investigator and/or Sponsor, placed the participant at unnecessary risk from continued administration of study intervention.
- The participant has a confirmed positive pregnancy test.
- Serious adverse experience related to study therapy or the occurrence of an adverse experience (clinical or laboratory) that, in the judgment of the investigator, warrants withdrawal of study therapy.
- If the QTc interval is >500 msec (based on either Fridericia or Bazett's correction), study therapy may be interrupted for up to 3 days with concomitant monitoring and correction of electrolytes. Study therapy may be resumed if QTc interval decreases to <500 msec.

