#### 8.3.3 **Electrocardiograms**

- Single 12-lead ECG will be obtained as outlined in the SoA using an ECG machine that automatically calculates the heart rate and measures PR, QRS, QT, and QTc intervals. Any clinically significant abnormality on study treatment must be followed until stabilization or return to baseline. Refer to Section 7.1 for QTc withdrawal criteria and additional QTc readings that may be necessary.
- For small participants whose size does not allow for a standard 12-lead ECG, a modified 12-lead ECG may be obtained.

Note: When the collection of vital signs, ECGs, and PK samples coincide, the blood samples for PK determination should be collected first (so that the PK samples are collected on time), followed by the vital signs, and then the ECG. It is preferred that the ECG be performed at the same time each day (eg, morning) to reduce diurnal variation.

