### 9.6.3 Safety Analysis

Safety and tolerability will be assessed by clinical review of all relevant parameters including AEs and laboratory parameters. The primary safety analysis will summarize the safety data for participants during the treatment period (IV and oral treatment phases) plus 14 days of

MK-5592-104-04 FINAL PROTOCOL

78

follow-up. Additional safety summaries will be presented in aggregate and by age cohort. No further summary breakdowns by formulations will be performed due to small sample sizes and potential of switching participants back and forth among formulations.

In this descriptive study, the primary safety endpoint of the proportion of participants with drug-related AEs will be provided along with the corresponding 95% CI. The 95% CIs for the safety parameters will be estimated using the Clopper-Pearson method, which is a conservative exact method of providing CIs in this single-arm study.

All other safety parameters will be summarized using descriptive statistics. These include the proportion of participants with the following safety parameters: (1) at least 1 AE; (2) an SAE; (3) a serious and drug-related AE; (4) an AE leading to discontinuation; (5) specific AEs by System Organ Class; and (6) predefined limits of change in specific laboratory parameters. In addition, vital signs, 12-lead ECGs, and standard laboratory safety tests at time points specified in the SoA will be summarized as change from baseline.

The analysis strategy for the safety parameters is summarized in Table 8.

Safety Endpoint	95% CI	Descriptive Statistics			
Any AE		X			
Any SAE		Х			
Any Drug-Related AE	Х	X			
Any Serious and Drug-Related AE		X			
Discontinuation due to AE		X			
Specific AEs, SOCs or PDLCs		X			
Change from Baseline Results (laboratory, ECGs, vital signs)		Х			
Abbreviations: AE=adverse event; CI=confidence interval; ECG = electrocardiogram; PDLC=Predefined Limit of Change; SAE=serious adverse event; SOC=System Organ Class; X=results will be provided.					

Table 8Analysis Strategy for Safety Parameters

Missing values will be handled using the Data-As-Observed approach; that is, any missing values will be excluded from the analysis.

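### QTc above 500 msec is the protocol's own action limit, but the analysis plan promises no count of children who cross it

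*Combined protocol and SAP*

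**What the plan says.** Section 2.3 lists the risks identified in product labeling as "hypersensitivity, hepatic toxicity, QTc prolongation, and drug interactions". Exclusion criterion 11 in Section 5.2 reads: "Has QTc prolongation (based on either Fridericia or Bazett's correction) at screening >500 msec". On treatment, Section 7.1 says: "If the QTc interval is >500 msec (based on either Fridericia or Bazett's correction), study therapy may be interrupted for up to 3 days". Under Section 8.3.3 the ECG machine "measures PR, QRS, QT, and QTc intervals", so the values are collected.

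The analysis side is Section 9.6.3. ECGs, with vital signs and laboratory tests, are covered by one sentence: "12-lead ECGs, and standard laboratory safety tests at time points specified in the SoA will be summarized as change from baseline". The list of participant-level proportions in the same section ends with "predefined limits of change in specific laboratory parameters". Table 8 puts ECGs in the change-from-baseline row, with descriptive statistics and no confidence interval. The missing-data rule is that "any missing values will be excluded from the analysis". Section 4.2.1.2 adds only that ECG parameters may be among the other assessments.

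The Schedule of Activities marks the 12-lead ECG at Screening, Day 1 (predose), Day 3, Week 1, Week 12, EOT and unscheduled visits. Nothing is marked at Weeks 2, 4, 6 or 9. Appendix 7 requires ECGs at every treatment visit in Italy.

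**The concern.** The protocol acts on an individual, absolute QTc value, while the plan summarizes group change. A child whose QTc passes 500 msec is the event of clinical interest, yet no planned output from the ECG data counts such children. Laboratory values are handled on both scales, change from baseline and predefined limits. QTc, also tied to a named risk, is promised only the first.

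Safety is the primary objective. Without a count from the measurements, a crossing of 500 msec is identified in the tables only through adverse event reporting. Appendix 3 makes an abnormal ECG an adverse event when the investigator considers it clinically significant. In an open-label single-arm study, an objective measurement with a numerical limit need not depend on that judgment alone.

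**Working it through.** **Inputs from the documents.** About 30 treated participants (APaT, Section 9.9.2), of whom about 20 in Age Cohort 1 and about 10 in Age Cohort 2 (Section 4.1). The limit is 500 msec (Sections 5.2 and 7.1). Intervals are two-sided 95% Clopper-Pearson (Table 10 footnote).

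**Assumptions.** The documents give neither an individual increase nor an SD of QTc change. I take an increase of 60 to 80 msec in the affected child, no change in the others, and an SD of change of 15 to 25 msec.

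**Step 1: the plan's own safety precision.** Table 10 gives upper limits for N=30. Two-sided Clopper-Pearson reproduces four of its five rows: 2/30 gives 22.1%, 5/30 gives 34.7%, 10/30 gives 52.8% and 15/30 gives 68.7%. The 0/30 row does not reproduce. The two-sided limit is 1 − 0.025^(1/30) = 11.6%. The printed 9.5% equals 1 − 0.05^(1/30), a one-sided limit, contrary to the footnote. That is a separate error, but it matters here because zero crossings is a plausible result.

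**Step 2: what a mean change shows.** The shift in a mean from k affected children is k × increase / n.

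| n | k | +60 msec | +80 msec |
|---|---|---|---|
| 30 | 1 | 60/30 = 2.0 | 80/30 = 2.7 |
| 30 | 2 | 120/30 = 4.0 | 160/30 = 5.3 |
| 20 | 1 | 60/20 = 3.0 | 80/20 = 4.0 |
| 10 | 1 | 60/10 = 6.0 | 80/10 = 8.0 |

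As a yardstick for noise (not a planned output), 1.96 × SD/√n at n=30 is 5.4 msec for SD 15, 7.2 for SD 20 and 8.9 for SD 25. At n=20 the range is 6.6 to 11.0, and at n=10 it is 9.3 to 15.5. Every shift in the table is smaller than the lowest yardstick for its n.

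**Step 3: absolute values.** Change from baseline does not carry the 500 msec scale. A child who enters just below the limit can cross it with a small change, and a large change can stay below it.

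**Step 4: which ECGs count.** Outside Italy, a prolongation between Week 1 and Week 12 can be recorded only at an unscheduled or EOT ECG. The schedule marks unscheduled ECGs, but 9.6.3 does not say whether they enter a summary organized by scheduled time points. A child who stops treatment should still attend visits (Sections 4.1 and 7.1), but a later ECG, such as Week 12, is then off drug.

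**Step 5: what a count would show.**

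| Crossings | Percent | 95% CI |
|---|---|---|
| 0/30 | 0.0% | 0 to 11.6% |
| 1/30 | 3.3% | 0.1 to 17.2% |
| 2/30 | 6.7% | 0.8 to 22.1% |
| 3/30 | 10.0% | 2.1 to 26.5% |

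If the true rate were 2%, 5% or 10% (assumed), the chance of at least one crossing among 30 children, 1 − (1 − p)^30, would be 45.5%, 78.5% or 95.8%.

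**The case against.** Much can be said for the plan, and several stronger readings fail.

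- A reader might infer that unscheduled ECGs are left out. The schedule's ECG row marks both EOT and unscheduled visits, so their handling is unclear rather than excluded.
- A reader might infer that a child taken off drug for QTc drops out of the Week 12 summary. Discontinued children are to complete the scheduled visits, an EOT visit with an ECG is due within 3 days, and 7.1 allows interruption followed by resumption. What stands is only that later ECGs may be off drug.
- A reader might say that Table 8 confines predefined limits to laboratory tests. Its row carries no such restriction; only the 9.6.3 text does.
- A reader might expect a falsely null result. The study tests no hypothesis and plans no interval for mean change. The statistics behind the descriptive summary are unspecified, so a maximum is neither promised nor ruled out. Insensitivity to one or two values is not bias.
- Affected children need not vanish from the report. Clinically significant ECG findings are adverse events, they feed the AE, SAE and discontinuation tables, and the external DMC reviews interim safety data.

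These points narrow the concern without removing it. None of them commits the final report to stating how many children crossed 500 msec.

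**Conclusion.** The point holds in limited form. QTc above 500 msec is the protocol's own numerical limit for a named risk, and the plan promises only a descriptive change summary for ECGs. One or two affected children of 30 would shift a mean by 2.0 to 5.3 msec under the assumed 60 to 80 msec increase, below the noise yardstick of 5.4 to 8.9 msec under the assumed SD. The core does not rest on those assumptions: a change summary does not report crossings of an absolute limit, whatever the SD. The documents do not support saying that the planned analysis is biased, that unscheduled ECGs or discontinued children are excluded, or that a prolongation would go unreported. This is an inexpensive improvement that should be made, not a flaw that invalidates the safety analysis.

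**What to change.** In Section 9.6.3 and Table 8, alongside the change-from-baseline summary:

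1. Add the number and percent of APaT participants with any on-treatment QTc above 500 msec by either Fridericia or Bazett, matching 7.1. Use all scheduled, unscheduled and EOT ECGs, with a two-sided Clopper-Pearson 95% CI. State that the EOT ECG counts as on-treatment and that later off-drug ECGs do not.
2. Add a descriptive summary of each participant's maximum increase from the Day 1 predose ECG, separately under each correction formula. Any cut-off for the increase (60 msec, for example) is the sponsor's choice and is not a document figure.
3. Repeat the count on the ECG visits common to all countries. A worst-value count rises with the number of ECGs per child, and Italy schedules more.
4. State whether unscheduled ECGs enter the change-from-baseline summary.

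The cost is SAP wording and a few table lines from ECGs already collected. No visit, procedure or sample size changes, and the clinical rule in 7.1 stays as it is. If no child crosses, report 0/30 with the two-sided upper limit of 11.6%, not the 9.5% printed in Table 10.

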# 9.6.4 Other Analyses

Palatability and acceptability of the POS PFS formulation, measured using a 5-point facial hedonic scale depicting various degrees of tolerance, will be summarized. The proportion of participants responding in each category to each of the questions on the first and on the last days of the PFS treatment phase will be tabulated.

## 9.7 Interim Analyses

There is no prespecified interim analysis planned for this open-label trial. However, interim reviews of safety and efficacy data will be conducted by the external DMC in accordance with its charter.

# 9.8 Multiplicity

No multiplicity adjustments are planned for this study.

# 9.9 Sample Size and Power Calculations

# 9.9.1 Efficacy Analysis

The sample size was chosen based on clinical considerations, not statistical ones. However, of interest is the precision of the estimates of efficacy. The width of the 95% CI for the global clinical response rate will depend on the size of the population and the number of participants who achieve a favorable clinical response. In a study completed in 2019 (P069) in 575 adults and adolescents to study efficacy and safety of POS versus VOR for the treatment of invasive aspergillosis, the favorable global clinical response rates at Week 6 and Week 12 for the participants on POS were 45% and 42%, respectively [Maertens, J. A., et al 2021].

Table 9 summarizes the observed global clinical response rate and the corresponding 95% CI for a variety of observed response rates for a population of 15 participants (the overall evaluable population).

Number of Participants in Population	Number Achieving Clinical Response	Observed Global Clinical Response	95% Confidence Interval a	
	9	60.0%	[32.3, 83.7]	
15	6	40.0%	[16.3, 67.7]	
	3	20.0%	[4.3, 48.1]	
a Confidence intervals are based on the Clopper-Pearson method [Clopper, C. J. and Pearson, E. S. 1934].				

Table 9Summary of Potential Observed Global Clinical Response Rates and95% Confidence Intervals

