#### Number of Participants:

Approximately 30 participants will be enrolled in the trial to achieve at least 15 participants in the Full Analysis Set (FAS) population (defined in Section 9.5.1) as characterized below.

Participants will be enrolled into the following age cohorts, which will enroll simultaneously:

• Age Cohort 1 (aged 2 to <12 years): approximately 20 participants enrolled to achieve at least 10 in the FAS population who transition to oral therapy (PFS or tablet) for at least 7 days after the end of IV treatment with POS.

• Age Cohort 2 (aged 12 years to <18 years): approximately 10 participants enrolled to achieve at least 5 in the FAS population who transition to oral therapy (PFS or tablet) for at least 7 days after the end of IV treatment with POS.

Intervention							
Groups	Treatment Name	Drug	Dose Strength	Dose Frequency	Route of Admin- istration	Regimen/ Treatment Period b	Use
	Posaconazole	Posaconazole IV a	18 mg/mL	QD, except BID on Day 1	IV infusion	Day 1: BID 6 mg/kg Day 2 through end of IV dosing: QD 6 mg/kg	duct
	Posaconazole	If weight ≤40 kg: Posaconazole PFS	30 mg/mL	QD	Oral	Days 8 – 84: weight-band dosing, see Table 1.	Test Proc
	Posaconazole	If weight >40 kg: Posaconazole Tablet	100 mg	QD	Oral	Days 8 – 84: 300 mg	
	Abbreviations: suspension; a: There is a ma BID, with u b: The posacon formulation indicated. Other current follows: MK-	BID = twice dail QD = once dail uximum dose of p to 300 mg IV azole IV formula s (PFS or tablet) or former na 5592; Noxaf	ly; IV = intravendy. 300 mg per admi in each dose. ation is to be adm may be administ ame(s) or alia fil; SCH 5659	ous; PFS = po nistration; on hinistered for a tered beginnin as(es) for s 92.	wder for de Day 1 only 1 minimum g on Day 8 tudy inte	elayed-release of , dosing frequen of 7 days; oral as clinically ervention(s)	al cy is are as
Total Number	There will be	a single inte	rvention arm				

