Specific procedures to be performed during the study, as well as their prescribed times and associated visit windows, are outlined in the SoA in Section 1.3. Details of each procedure are provided in Section 8.

Approximately 30 participants will be enrolled to achieve at least 15 participants as characterized below in the FAS population (Section 9.5.1). Participants will be enrolled into the following age cohorts, which will enroll simultaneously:

- Age Cohort 1 (2 years to <12 years of age): approximately 20 participants enrolled to achieve at least 10 in the FAS population who transition to oral therapy (PFS or tablet) for at least 7 days after the end of IV treatment with POS.
- Age Cohort 2 (12 years to <18 years of age): approximately 10 participants enrolled to achieve at least 5 in the FAS population who transition to oral therapy (PFS or tablet) for at least 7 days after the end of IV treatment with POS.

For ongoing safety evaluations and to ensure safe study conduct, an independent, external DMC will be established. Specific details regarding the DMC will be described in the DMC charter.

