# 8.2 Efficacy/Immunogenicity Assessments

# 8.2.1 Global Clinical Response

The investigator will assess global clinical response at the Week 6 and Week 12 visits; in the event of early therapy discontinuation, global clinical response will be assessed at the EOT Visit. All data related to the evaluation of global clinical response will be collected, including clinical signs and symptoms, imaging, serologic testing, and fungal culture and histology. A global clinical response will be assessed by the investigator as favorable (positive) if the participant is alive and has a complete or partial response, using the definitions of responses to therapy and study outcomes in clinical trials of invasive fungal diseases at the time points of interest [Segal, B. H., et al 2008] (Table 6).

Outcome, Response	Definition		
Success			
Complete response	Survival within the prespecified period of observation, resolution of all attributable symptoms and signs of disease, resolution of radiological lesion(s), and documented clearance of infected sites that are accessible to repeated sampling.		
Partial response	Survival within the prespecified period of observation, improvement in attributable symptoms and signs of disease, improvement of radiological lesion(s) a , and evidence of clearance of infected sites that are accessible to repeated sampling. In the case of radiological stabilization b , resolution of all attributable symptoms and signs of fungal disease; or where biopsy of an infected site shows no evidence of hyphae; or where culture is negative.		
Failure			
Stable response	Survival within the prespecified period of observation and minor or no improvement in fungal disease; or persistent isolation of Aspergillus spp or histological present in infected sites.		
Progression of fungal disease	Worsening of clinical symptoms and signs of disease plus new sites of disease or radiological worsening; or persistent isolation of Aspergillus spp from infected sites.		
Death	Death during the prespecified period of evaluation, regardless of attribution.		

a Improvement of radiological lesions is defined as at least 25% reduction in diameter of radiological lesion.

b Radiological stabilization is defined as 0%-25% reduction in the diameter of the lesion.

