### 9.1 Statistical Analysis Plan Summary

Key elements of the statistical analysis plan are summarized below; the comprehensive plan is provided in Sections 9.2 through 9.12.

Study Design Overview	A Phase 2, Open-Label, Non-Comparative Clinical Trial to Study the Safety and Efficacy of Posaconazole (POS, MK-5592) in Pediatric Participants Aged 2 to Less Than 18 Years With Invasive Aspergillosis
Treatment Assignment	Pediatric participants aged 2 to <18 years with IA will be allocated to receive POS (Day 1-7 IV formulation, Day 8-84 either IV, PFS or oral formulation). Participants will be enrolled into 2 age cohorts: Age Cohort 1 (2 to <12 years) or Age Cohort 2 (12 to <18 years).
Analysis Populations	Safety: All Participants as Treated (APaT).
	Efficacy:
	
 
Full Analysis Set (FAS) and
 
Responder Population
 

	Pharmacokinetics : All treated participants who receive at least 7 days of POS IV solution and have postdose PK sampling while on POS IV therapy (PK Analysis Population).
	Analysis populations are also defined in Section 9.5.
Primary Endpoint(s)	The primary safety endpoint is the proportion of participants in the APaT population who experience 1 or more treatment-related AEs during POS study treatment (IV or oral) plus 14 days of follow-up.
	There are no primary efficacy or pharmacokinetic endpoints.
Secondary Endpoints	• Proportion of participants in the FAS population with a favorable global clinical response (partial or complete response) at the Week 6 (Day 42) Visit, at the Week 12 (Day 84) Visit, and at the EOT Visit (if different).
	• Proportion of participants in the Responder Population who have a relapse of IA at any point after achieving favorable global clinical response through 28 days post-treatment.
	• Cmin, Cmax, and Tmax, based upon sparse PK sampling (peak and trough concentration).
	• Analysis of exposure-response (efficacy and safety) relationships.
	
 
Participants' categorical perception of palatability and acceptability of the PFS formulation.
 

Statistical Methods for Efficacy/Immunogenicity/ Pharmacokinetic Analyses	Efficacy endpoints- overall proportion of participants in the FAS population with a favorable global clinical response at the Week 6, the Week 12, and the EOT Visits – will be estimated and the corresponding 95% confidence interval (CI) provided using the Clopper-Pearson method.

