# 9.5 Analysis Populations

# 9.5.1 Efficacy Analysis Populations

The FAS population will serve as the primary population for the analysis of global clinical response data in this study. The efficacy analysis population to be studied (possible, probable, or proven IA) is similar to the population used for the primary efficacy analyses conducted in the adult study (P069) of invasive aspergillosis. The FAS population consists of all allocated participants who:

- have possible, probable, or proven IA (based on modified 2020 EORTC/MSG definitions) as classified by the investigator,
- receive at least 1 dose of study treatment,
- have at least 1 post-allocation observation for the analysis endpoint subsequent to at least 1 dose of study treatment, and
- have baseline data for those analyses that require baseline data.

The Responder Population will serve as the population for the analysis of relapse.

• The Responder Population consists of participants from the FAS population who have achieved a favorable global clinical response at the end of study treatment.

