### 9.9.2 Safety Analysis

The primary safety analysis will summarize the safety data for participants during the treatment period (IV and oral treatment phases) plus 14 days of follow-up.

The APaT population is expected to include approximately 30 participants. The estimate of and the upper bound of the 95% CI for the underlying percentage of participants with a specific AE, given various hypothetical observed number of participants with that specific

AE within the study, are provided in Table 10. These calculations are based on the exact binomial method proposed by Clopper and Pearson.

Ν	Hypothetical Number of Participants with AE	Estimate of Incidence	95% CI Upper Limit a
	0	0.0%	9.5%
	2	6.7%	22.1%
30	5	16.7%	34.7%
	10	33.3%	52.8%
	15	50.0%	68.7%

Table 10Estimate of Incidence of a Specific AE and Upper Limit of 95% CI Based on aHypothetical Number of Participants with that Specific AE

Abbreviations: AE=adverse event; CI = confidence interval.

a Based on the 2-sided exact 95% confidence interval (CI) on a binomial proportion [Clopper, C. J. and Pearson, E. S. 1934].

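### Does Table 9 show efficacy precision for the wrong population by using 15 participants when response is analysed in the whole FAS?

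*Combined protocol and SAP*

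**What the plan says.** Section 9.9.1 says the trial's size rests on clinical rather than statistical grounds, adds that the precision of the efficacy estimates is still of interest, and states that interval width depends on both the population size and the number of responders. Table 9 then gives three intervals "for a population of 15 participants (the overall evaluable population"). Its footnote states the method: "Confidence intervals are based on the Clopper-Pearson method".

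The Synopsis gives the source of the 15: "Approximately 30 participants will be enrolled in the trial to achieve at least 15 participants in the Full Analysis Set (FAS) population". Section 4.1 repeats the target and divides it by age cohort. Cohort 1 needs "at least 10 in the FAS population who transition to oral therapy (PFS or tablet) for at least 7 days", and Cohort 2 needs at least 5 on the same terms.

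The response endpoint in Section 9.1 is the "Proportion of participants in the FAS population with a favorable global clinical response (partial or complete response"). Section 9.5.1 admits to the FAS participants with possible, probable or proven IA who receive at least one dose, "have at least 1 post-allocation observation for the analysis endpoint subsequent to at least 1 dose of study treatment", and have baseline data where an analysis needs it. Oral transition is not a condition. For safety, Section 9.9.2 states an expected number: "The APaT population is expected to include approximately 30 participants". Section 9.9.1 gives no corresponding figure for the FAS.

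**The concern.** Table 9 is the only statement of efficacy precision in the plan, and its N is not the N of the planned analysis. The 15 is the sum of two cohort minimums, each restricted to FAS members who move to oral therapy and stay on it. The response analysis takes the whole FAS.

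That FAS should be larger than 15. IA is an entry criterion, so the diagnostic condition removes few or none. Early stoppers still yield an observation, since "in the event of early therapy discontinuation, global clinical response will be assessed at the EOT Visit". Death is a failure category in Table 6, so it need not mean a missing outcome. About 30 participants are expected to be treated.

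The label adds to the difficulty. It suggests that 15 is the total to be evaluated, not a floor, and Section 9.5 defines no population of that name. A reader could conclude that half of the enrolled participants will be left out of the efficacy analysis, or that the trial will estimate response less precisely than it probably will.

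**Working it through.** **Inputs.** From Table 9: n = 15 with 9, 6 and 3 responders. From the Synopsis and Section 4.1: the floor is 10 + 5 = 15, with about 30 enrolled. From Section 9.9.2: about 30 treated. Only 15 and about 30 come from the documents; n = 20 and n = 25 are assumed intermediate values.

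**Formula.** For x responders out of n, the two-sided 95% Clopper-Pearson limits are

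- lower = the 0.025 quantile of Beta(x, n − x + 1)
- upper = the 0.975 quantile of Beta(x + 1, n − x)

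**Step 1: reproduce Table 9.**

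- 9/15: lower from Beta(9, 7), upper from Beta(10, 6), giving [32.3, 83.7]
- 6/15: lower from Beta(6, 10), upper from Beta(7, 9), giving [16.3, 67.7]
- 3/15: lower from Beta(3, 13), upper from Beta(4, 12), giving [4.3, 48.1]

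All three rows agree with the plan to one decimal, and the binomial tail at each limit is 0.025. The arithmetic is not in question.

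**Step 2: repeat for larger FAS sizes.** Widths are in percentage points and come from unrounded limits.

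| n | 20% observed | width | 40% observed | width | 60% observed | width |
|---|---|---|---|---|---|---|
| 15 | 3/15 [4.3, 48.1] | 43.8 | 6/15 [16.3, 67.7] | 51.4 | 9/15 [32.3, 83.7] | 51.4 |
| 20 | 4/20 [5.7, 43.7] | 37.9 | 8/20 [19.1, 63.9] | 44.8 | 12/20 [36.1, 80.9] | 44.8 |
| 25 | 5/25 [6.8, 40.7] | 33.9 | 10/25 [21.1, 61.3] | 40.2 | 15/25 [38.7, 78.9] | 40.2 |
| 30 | 6/30 [7.7, 38.6] | 30.9 | 12/30 [22.7, 59.4] | 36.7 | 18/30 [40.6, 77.3] | 36.7 |

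At 40% or 60%, 51.4/36.7 = 1.40, so Table 9's intervals are about 40% wider than those from a FAS of 30. At 20% the ratio is 43.8/30.9 = 1.42.

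**Step 3: is 15 a valid floor for the FAS?** Every one of the 15 must belong to the FAS and also complete the oral transition. Adding FAS members who never transition can only raise the count. If the enrolment target is met, FAS ≥ 15. At each response rate shown, width falls as n rises, so n = 15 is the least precise case.

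**Step 4: what uses Table 9?** Section 9.3 states no hypotheses, Section 9.8 plans no multiplicity adjustment, and efficacy is a secondary objective. No power figure, success threshold or stopping rule refers to the table. Section 9.6.1 computes the reported intervals from the observed data.

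**The case for a change.** The strongest case for a change is that, in a trial that only estimates, the precision statement is the whole statistical content of the efficacy sample-size section. It should therefore describe the analysis that will be run. Section 9.9.2 gives an expected N for safety, and Section 9.9.1 could have done so for the FAS. Nothing in Section 9.9.1 marks 15 as a minimum, and the possible overstatement of width, 40 to 42%, is not small.

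The factual part of this stands: the label is loose, no expected FAS size is given, and the reader has to go to Section 4.1 to learn what 15 means. The consequence does not follow. The Synopsis ties the 15 to the FAS as a minimum, and Section 9.9.1 itself says that width varies with population size. An optimistic N would be a different matter, because it would promise precision the trial might not deliver; this one promises less than is likely.

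It can also be argued that fewer participants may contribute at Week 12 than at the end-of-treatment visit, so one value of n cannot serve every time point. The documents point both ways. Section 8.2.1 sends early stoppers to the end-of-treatment assessment, while Sections 4.1 and 7.1 expect visits to continue after treatment stops. If numbers at Week 12 do fall, they move towards the 15 already tabulated, which makes it a more reasonable planning value.

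**Conclusion.** The mismatch is real but is a slip of labelling, and no change to the plan is needed. Table 9 is a correct illustration at the planned minimum. With a FAS between 15 and about 30, the 95% interval at 40% response would be between 51.4 and 36.7 points wide, and the plan shows the cautious end of that range. More rows would improve presentation but would not alter enrolment, the analysis populations, the analyses, the reported intervals or any conclusion. Analysts will take the FAS from Section 9.5.1 and use the number actually available.

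This rests on two assumptions: that the target of 10 plus 5 is met, and that at least 15 FAS members contribute a response at the time point in question. If either fails, the reported interval could be wider than Table 9 shows, and it would still be calculated from the actual count.
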